#### **12.2.9.4. Analysis of Laboratory Analytes**

Laboratory measurements collected at scheduled visits will be listed by patient by visit using all randomized patients. An additional listing will be presented for all laboratory measurements that are outside the SI units (International System of Units) normal range. Baseline for calcitonin, ALT, and hemoglobin A1c, will be Visit 1 and for serum creatinine, urine ACR and lipids will be Visit 3. All summary analyses will be based on the ITT population. Laboratory measurements that fall within a visit window will be associated with that visit. The laboratory measurement within the window that was taken closest to the visit date will be representative of that patient's lab value for that visit.

Unless otherwise specified, continuous laboratory measures will be analyzed using an ANOVA model on the rank-transformed data. The model includes treatment. Treatment group comparisons will be performed with no multiplicity adjustment. Categorical laboratory measures will be analyzed using Chi-square tests or Fisher's exact tests. For lipids (total cholesterol, LDL-C, HDL-C, triglycerides, and non-HDL-C) the summary analysis will be conducted based on the percentage change from baseline using an ANOVA model described above. The change from baseline will be used for the ratio of total cholesterol to HDL-C.

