For subgroup analyses, all tests of interactions between treatment groups and other factors will be conducted at a nominal 2-sided alpha level of 0.10 and will be deemed to be exploratory. No adjustment for multiplicity will be performed unless otherwise specified.

Countries in similar geographic regions with <10 patients will be pooled in order to achieve a pooled country of at least 10 patients. All analyses using country in the model will use pooled country, unless otherwise specified. The final pooling by country and geographic region will be specified prior to data lock.

The baseline is Visit 3. If baseline data are missing, the last measurement taken prior to this visit will be used for the baseline measurement.

The primary analysis and key secondary CV endpoint analyses will be based on adjudicated events that occurred after randomization (Visit 3). Sensitivity analyses may be conducted

including events reported by investigators or events identified through safety reviews, to assess their impact on the primary analysis results.

All analyses will be implemented using SAS Version 8.2® or higher.

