The proportion of patients with microalbuminuria or macroalbuminuria at baseline or during the study will be compared between treatment groups at by visit. Shift tables will be presented for urine ACR. The tables will show the proportions of patients with shifts in the laboratory results from baseline to maximum post-baseline result using categories based on the Central Laboratory reference ranges. The categories for urine ACR will be ≤ 30 mg/g, >30 mg/g to ≤ 300 mg/g and >300 mg/g. Shifts will be grouped to show the proportions of patients who experienced decreases (post-baseline category $<$ baseline category), increases (post-baseline category $>$ baseline category), or no change from baseline to maximum post-baseline result for each treatment. Baseline will be the last non-missing observation in the study period from screening to randomization (Visit 1 through Visit 3). The maximum post-baseline result in the postbaseline study period (Visits 3 and beyond) will be the maximum result for the analysis. The analyses will use both scheduled and unscheduled labs and will be in all randomized patients with at least 1 baseline and 1 post-baseline urine ACR measurement.

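### The urine ACR shift table counts Visit 3 as both baseline and post-baseline, so a patient whose baseline is a Visit 3 value can never be shown as decreasing

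*SAP*

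**What the plan says.** SAP 4.17.3 (Laboratory Analytes) sets up the urine ACR shift table as follows.

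- **Baseline:** "Baseline will be the last non-missing observation in the study period from screening to randomization (Visit 1 through Visit 3", closing the parenthesis at Visit 3. If a Visit 3 value exists, it is the baseline.
- **Quantity tabulated:** "shifts in the laboratory results from baseline to maximum post-baseline result".
- **Post-baseline window:** "The maximum post-baseline result in the postbaseline study period (Visits 3 and beyond) will be the maximum result for the analysis".
- **Categories:** up to 30 mg/g, above 30 and up to 300 mg/g, and above 300 mg/g.
- **Grouping:** "Shifts will be grouped to show the proportions of patients who experienced decreases", with increases and no change as the other two groups. A decrease means that the post-baseline category is below the baseline category.
- **Analysis set:** the analyses "will be in all randomized patients with at least 1 baseline and 1 post-baseline urine ACR measurement", using scheduled and unscheduled samples.

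Elsewhere, SAP 4.2 states the general rule, "The baseline is Visit 3", and falls back to an earlier measurement if that one is missing. Protocol 12.2.9.4 sets Visit 1 as baseline for calcitonin, ALT and HbA1c, but says that baseline "for serum creatinine, urine ACR and lipids will be Visit 3".

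**The concern.** The two windows share Visit 3. Where a Visit 3 ACR exists, one measurement serves as the reference value and as a candidate for the value compared with it. Because the comparison uses a maximum, the overlap acts in one direction only: it stops the post-baseline result from falling below baseline. The table would then report decreases by arm although, for these patients, the rule does not allow one. A zero produced by the definition could be read as a finding that nobody improved.

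The overlap also weakens the inclusion rule. One Visit 3 sample counts as the baseline measurement and as the post-baseline measurement, so a patient with no follow-up ACR enters the table as no change.

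**Working it through.** The plan gives no figure to reproduce. The check is logical, with a small enumeration.

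**1. The rule as written.** Let b be the Visit 3 ACR, which is the baseline (SAP 4.17.3; Protocol 12.2.9.4). Let m be the highest value after Visit 3. The post-baseline window contains Visit 3, so the tabulated result is M = max(b, m) ≥ b. The three categories are ordered in ACR, so category(M) ≥ category(b). A decrease requires category(M) < category(b), which cannot happen.

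**2. Enumeration.** With k values after Visit 3 and three categories (coded 0, 1, 2), there are 3^(k+1) possible category sequences. If only values after Visit 3 count, a decrease needs all k of them below b. The number of such sequences is 0^k + 1^k + 2^k = 1 + 2^k.

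| k later values | Sequences | Decreases as written | Decreases using only values after Visit 3 |
|---|---|---|---|
| 1 | 9 | 0 | 3 |
| 2 | 27 | 0 | 5 |
| 3 | 81 | 0 | 9 |
| 7 | 6561 | 0 | 129 |

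These are counts of possible patterns, not expected proportions of patients.

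**3. One constructed patient.** Visit 3 ACR 400 mg/g, then 100 and 80. As written, M = max(400, 100, 80) = 400, the same category as baseline: no change. Using later values only, the maximum is 100, one category lower: a decrease.

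**4. Increases.** category(max(b, m)) > category(b) holds exactly when category(m) > category(b). The count of increases is therefore the same under both rules, and the overlap only moves decreases into no change.

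**5. Denominator.** If u patients have a Visit 3 value and nothing later, they are counted as no change. With I increases among n patients who have real follow-up, the reported proportion is I/(n + u) instead of I/n. The documents do not give u.

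**6. Illustration under assumed values.** The documents give no ACR distribution. I assumed lognormal ACR with median 15 or 30 mg/g, between-patient log SD 1.2, within-patient log SD 0.5 or 0.8, a treatment shift of 0 or −0.3 on the log scale, and a Visit 3 value for every patient.

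| Later values | Decrease, as written | Decrease, corrected |
|---|---|---|
| 1 | 0% | 8.2% to 20.8% of all patients |
| 6 | 0% | 1.6% to 5.0% of all patients |

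The proportion with an increase was identical under the two rules in every scenario.

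**7. Who is affected.** A patient whose last pre-randomization ACR is from Visit 1 or 2, with none at Visit 3, has a baseline outside the post-baseline window. Steps 1 to 3 do not apply to that patient, and a decrease can be shown.

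**The case against.** **The wording can be read kindly.** The sentence speaks of a post-baseline result, the inclusion rule asks separately for a baseline and a post-baseline measurement, and a decrease group is defined. A reading that gives all of these effect would leave out the baseline record. That is probably the intent. But the parenthesis names Visit 3 as part of the post-baseline period, no sentence excludes the baseline record, and a programmer following the text would produce the overlap.

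**ACR may not be collected at Visit 3.** In the extracted Study Schedule (Protocol Attachment 1), the ACR row has a mark at Visit 1 and the next at about Visit 6. The columns are unreliable: the later lipid marks fall at Visits 8 and 14, whereas SAP 4.17.3.1 gives 24 and 60 months, which are Visits 9 and 15. Still, moving the later ACR marks by one column would not put one at Visit 3. Against this, Protocol 12.2.9.4 names Visit 3 as the ACR baseline in contrast to Visit 1 for other tests, and the table admits unscheduled samples. What stands is that the share of affected patients cannot be determined from the documents. It could be small or nearly everyone.

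**A maximum-based table is built to show worsening.** This also stands. Even when corrected, a decrease requires every later value to lie in a lower category, so decreases will be uncommon when there are several follow-up samples. The plan nonetheless chose to report them, and uncommon differs from impossible.

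**A stronger reading to avoid.** A reader might infer that the trial would record any regression of albuminuria on dulaglutide as no change. The documents do not support that. Patients with a Visit 1 or 2 baseline can still show a decrease here. SAP 4.17.3 separately compares micro- and macroalbuminuria proportions between arms by visit, and SAP 4.3.2 gives a rank-based ANOVA for continuous laboratory values. Neither uses this window.

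**Conclusion.** The rule is wrong as written, with a narrow reach. For every patient whose baseline is a Visit 3 ACR, the decrease group is unreachable, a true decrease is reported as no change, and a patient with no follow-up ACR is counted as having one. This follows from the two definitions alone and needs no assumption about the data.

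The number of patients affected does rest on something unsettled, namely whether ACR was measured at Visit 3. The percentages in the illustration rest entirely on assumed distributions and show only that the lost cell need not be trivial.

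The effect is limited to the decrease and no-change cells and the denominator of one descriptive safety table. Increase counts are unchanged, although their percentages would be diluted by any patients with a Visit 3 value only. The microvascular endpoint, alpha, power and the primary analysis are untouched.

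**What to change.** In SAP 4.17.3, replace the parenthesis that defines the post-baseline period with measurements taken after the baseline record, that is, after Visit 3 (randomization). Require at least one such value for a patient to enter the shift table. Confirm against the original Study Schedule whether ACR is collected at Visit 3, so that the baseline visit named in Protocol 12.2.9.4 and the collection schedule agree.

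The cost is one phrase in the SAP and one condition in the table program. No new data are needed, and no other analysis changes.

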4.17.3.1. Lipid Parameters

The following lipid parameters will be assessed for all randomized patients:

- total cholesterol
- high-density lipoprotein cholesterol (HDL-C)
- low-density lipoprotein cholesterol (LDL-C)
- non-HDL-C (total cholesterol minus HDL-C)
- ratio of total cholesterol to HDL-C (total cholesterol divided by HDL-C)
- triglycerides

Fasting lipids will be collected at randomization (Visit 3) and after 24 and 60 months of treatment (Visit 15). Visit 3 will be considered as baseline for these analyses. Analyses of the percent change from baseline to each visit and to last measurement will be performed separately

for each marker. Analyses of change from baseline to each visit and to last measurement will be performed for the ratio of total cholesterol to HDL-C. The median will be reported for triglycerides since the data are not expected to be normally distributed; and the mean will be reported for the other lipid parameters. Patients will be required to have a baseline and a postbaseline measurement of the marker to be included in these analyses.

4.17.4. Vital Signs

Vital signs (systolic blood pressure, diastolic blood pressure, and heart rate) will be collected in the seated position in triplicate at each office visit. Measurements will be averaged for each patient at each visit; the average values will be used in the descriptive summaries and analyses.

All averaged measurements will be listed by patient by visit using all randomized patients.

Descriptive statistics for the averaged measurements and change from baseline by treatment arm and visit will be presented. Summary analyses will be conducted using the ITT population. The change from baseline will be analyzed using the MMRM model.

4.17.5. ECG Analyses

Electrocardiograms will be performed for all randomized patients at each visit. Both scheduled and unscheduled ECGs will be qualitatively evaluated by an ECG reading center. The qualitative characteristics assessed will be summarized in the major categories and subcategories of findings: normal ECG, abnormal ECG findings, and the subcategories of abnormal findings.

The number of patients in each category and subcategory will be compared between treatment groups and by visit using a Chi-square or Fisher's exact tests.

5. Unblinding Plan

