### **7.1.3. Randomization (Visit 3)**

Patients who are adherent to study drug during the run-in period and who still meet eligibility criteria will be randomized, while those not adherent to study drug during the run-in will not participate further.

For patients who remain eligible to be randomized, vital signs and waist and hip circumference will be measured, an electrocardiogram (ECG) will be recorded, and samples will be collected as outlined in the Study Schedule ([Attachment 1](#)). Laboratory samples that need to be drawn fasting should be drawn after an 8-hour fasting period. Patients will be administered the cognitive function tests (that is, MoCA and DSST); men will complete the erectile function questionnaire (that is, IIEF). Concomitant medications, preexisting conditions, AEs, injection instructions, and adherence to study drug and lifestyle interventions will be reviewed.

Patients will be instructed to remain on their antihyperglycemic therapy except where adjustments may be needed to minimize the risk of hypoglycemia (Section 9.5.2.1.1). If the screening HbA1c value is <7.0% and if the patient is taking insulin, a sulfonylurea or a meglitinide, the total daily dose of insulin may be reduced by 15%, the total daily dose of sulfonylurea may be reduced by 1 dose level, and the mealtime dose of meglitinide may be reduced by 1 dose level or discontinued.

Patients will be randomized to 1 of the following treatment arms:

- 1) placebo: once-weekly subcutaneous placebo injection
- 2) dulaglutide: once-weekly subcutaneous dulaglutide (1.5 mg) injection

Patients will be instructed to inject study drug, on the same day at approximately the same time, each week (that is, to continue on the same schedule used during the run-in period). Patients should be instructed to contact the investigative site for assistance as soon as possible if they experience any difficulties administering the study medication. Patients should be advised about the appropriate course of action in the event that study drug is not taken at the required time (see

Section 9.5.1). Used syringes should be placed in the sharp items container provided to patients. Adherence to study drug will be emphasized.

Self-monitored blood glucose (SMBG) testing supplies will be dispensed, the measurement technique will be reviewed, and patients will be advised regarding the frequency of SMBG testing according to their other medications and the investigator's clinical judgment.

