- If age  $\geq 55$  years and subclinical vascular disease defined as 1 or more of the following:
  - a history of myocardial ischemia by a stress test or with cardiac imaging, with or without history of exertional angina
  - $>50\%$  vascular stenosis with imaging of the coronary, carotid, or lower extremity arteries, with or without claudication history
  - ankle-brachial index  $<0.9$
  - 2 consecutive values or a documented history of persistent  $eGFR < 60$  mL/minute/1.73m^2
  - a history of hypertension with documented LV hypertrophy on an ECG or echocardiogram
  - documented history of persistent microalbuminuria, or macroalbuminuria; or 2 consecutive urine samples demonstrating micro- or macroalbuminuria;

OR

- If age  $\geq 60$  years and at least 2 or more of the following risk factors for CV outcomes:
  - current tobacco use (any form of tobacco)
  - use of at least 1 approved lipid modifying therapy to treat hypercholesterolemia or a documented untreated low-density lipoprotein cholesterol (LDL-C)  $\geq 3.4$  mmol/L (130 mg/dL) within the past 6 months

- documented treated or untreated high-density lipoprotein cholesterol (HDL-C) <1.0 mmol/L (40 mg/dL) for men and <1.3 mmol/L (50 mg/dL) for women or triglycerides  $\geq$ 2.3 mmol/L (200 mg/dL) within the past 6 months
  - use of at least 1 blood pressure medication to treat hypertension or untreated systolic blood pressure (SBP)  $\geq$ 140 mm Hg or diastolic blood pressure (DBP)  $\geq$ 95 mmHg
  - measured waist-to-hip ratio >1.0 for men and >0.8 for women
- [6] Body mass index  $\geq$ 23 kg/m^2
- [7] Adherence to study drug during the run-in period is 100%
- [8] In the investigator's opinion, are well-motivated, capable, and willing to self-inject study treatment once weekly, as required for this protocol
- [9] Have given written informed consent to participate in this study in accordance with local regulations and Ethical Review Board (ERB) governing the study site

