#### **10.2.2.7. Adverse Event of Interest: Clinically Significant Supraventricular Arrhythmias and Cardiovascular Conduction Disorders**

All events of supraventricular arrhythmias and cardiovascular conduction disorders will be prospectively collected and evaluated.

Patients who develop supraventricular arrhythmias or cardiovascular conduction disorders should undergo an ECG and diagnostic tests to determine exact diagnosis. The specific diagnosis will be recorded as an AE or SAE. All supraventricular arrhythmias and cardiovascular conduction disorders deemed clinically significant by the investigator will be listed as SAE's. Study drug should be temporarily discontinued in any patient with signs and symptoms of serious cardiac arrhythmias or conduction disorders. Study drug may be restarted when/if it is safe to do so, in the opinion of the investigator.

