#### **10.2.3.3. ECGs**

Twelve-lead ECGs will be obtained according to Study Schedule ([Attachment 1](#)). ECGs should be recorded after the patient has been supine for 5 minutes in a quiet room.

The ECGs must be interpreted by a qualified physician (the investigator or designee) at the site as soon after the time of ECG collection as possible, and ideally while the patient is still present, for immediate patient management, if needed. The investigator or designee must document their review of the ECG. If a clinically relevant abnormality is observed on the patient's ECG, then the investigator should assess the patient for symptoms (such as palpitations, near syncope, syncope, chest pain).

The 12-lead ECGs also will be assessed by the independent ECG reading center. The purpose of the qualitative review is to identify electrocardiographic abnormalities consistent with MI or myocardial ischemia, as well as other abnormalities (for example, arrhythmias). The original ECG will be retained at the investigative site. The ECG tracing also will be submitted either electronically (original) or on paper (that is, a copy) via traceable courier to the ECG reading center. Each 12-lead ECG will be evaluated qualitatively and will be compared to the prior time point. All ECG findings of new, postbaseline MI/myocardial ischemia not clearly associated with a previously reported MI will be considered as a potential silent MI endpoint. The site will be notified and further information ascertained. As appropriate, all new endpoint events of

MI/myocardial ischemia not already reported by the site will be submitted for adjudication as a possible silent MI as described in the CEC Charter.

The ECG Charter will describe the methodology employed in the acquisition and expert analysis of 12-lead ECGs. The CEC Charter will contain the final detailed event definition for silent MI used for adjudication. Study sites will be requested to send appropriate documentation to the CEC in a timely fashion for adjudication of the event.

The investigator or qualified designee's interpretation will prevail for immediate patient management purposes, and the ECG reading center's interpretation will prevail for data analysis purposes.

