#### **12.2.9.6. ECG Analyses**

Both scheduled and unscheduled ECGs at each visit will be listed for all randomized patients. The ECGs will be qualitatively evaluated (see Section 10.2.3.3). The qualitative characteristics assessed will be summarized in the major categories of findings: normal ECG, abnormal ECG findings, and the subcategories of abnormal findings. The number of patients in each category will be compared between treatment groups and by visit using a Chi-square or Fisher's exact test.

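### The ECG safety comparison ignores the Visit 3 tracing, which dilutes any effect on new findings, most for findings common at entry; add a comparison of new findings

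*SAP*

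**What the plan says.** SAP 4.17.5 sorts each ECG, scheduled or unscheduled, into "normal ECG, abnormal ECG findings, and the subcategories of abnormal findings", and then: "The number of patients in each category and subcategory will be compared between treatment groups and by visit using a Chi-square or Fisher's exact tests". Protocol 12.2.9.6 plans the same test: "The number of patients in each category will be compared between treatment groups and by visit using a Chi-square or Fisher's exact test". Neither section limits the count to findings absent at randomization, defines a new or treatment-emergent ECG finding, or plans a shift table. The SAP default for post-baseline categorical variables (4.3.3) does not supply the restriction; it asks only that a measurement exist.

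The material for a baseline-referenced count is already collected. At Visit 3, protocol 7.1.3 states that "an electrocardiogram (ECG) will be recorded, and samples will be collected as outlined in the Study Schedule". For the reading center, protocol 10.2.3.3 states: "Each 12-lead ECG will be evaluated qualitatively and will be compared to the prior time point". The same section gives the reading center's interpretation precedence for data analysis.

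Elsewhere the SAP does refer back to baseline: adverse events are treatment-emergent only if worse than at baseline (4.17.2), urine ACR has shift tables (4.17.3), lipids are analyzed as change or percent change (4.17.3.1), and vital signs, including heart rate, as change from baseline by MMRM (4.17.4).

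**The concern.** The safety question is whether dulaglutide produces new ECG abnormalities. The planned test asks whether, at a given visit, the arms differ in the total number of patients showing a finding, old and new together. Findings already present at randomization cannot depend on treatment. They add the same expected amount to both arms, which pulls the risk ratio toward 1 and adds variance.

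Some patients will enter with abnormal tracings. Prior MI and myocardial ischemia are qualifying conditions, and so is "a history of hypertension with documented LV hypertrophy on an ECG or echocardiogram" (protocol 8.1).

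Supraventricular arrhythmias and conduction disorders are a prespecified safety objective. SAP 4.17.5 is the only planned between-arm comparison of centrally read rhythm and conduction findings. If such a finding is fairly common at entry, a real increase in new cases could appear as a small, non-significant difference.

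**Working it through.** The documents state no rate, power or sample size for the ECG test, so there is no plan figure to reproduce. Everything below rests on assumed rates.

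**Inputs**
- Two-sided alpha 0.05 (SAP 4.2) and 1:1 allocation (protocol 9.3).
- About 9600 randomized (protocol 7.1), so 9600/2 = 4800 per arm. Assumed ECGs at one visit: n = 4000 per arm.
- Assumed: p0 = prevalence of the finding at Visit 3, with such findings persisting; new-finding proportion among the rest q = 2% on placebo and 3% on dulaglutide (true risk ratio 1.5).

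**Formulas**
- Planned test, n per arm: placebo proportion p0 + (1 − p0) × 0.02; dulaglutide proportion p0 + (1 − p0) × 0.03.
- New-findings test, n(1 − p0) per arm: 0.02 against 0.03.
- Power ≈ Φ(d/SE − 1.96), with d the difference and SE = √[(pA(1 − pA) + pB(1 − pB))/m], where m is the number per arm in that test.

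**Worked case, p0 = 10%**
- Planned: 0.10 + 0.90 × 0.02 = 0.118 and 0.10 + 0.90 × 0.03 = 0.127; d = 0.009. SE = √[(0.1041 + 0.1109)/4000] = 0.00733. Power = Φ(1.23 − 1.96) = Φ(−0.73) = 23%.
- New findings: m = 3600, d = 0.010. SE = √[(0.0196 + 0.0291)/3600] = 0.00368. Power = Φ(2.72 − 1.96) = Φ(0.76) = 78%.

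**Across baseline prevalence**

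| Prevalence at Visit 3 | Visit proportions | Visit risk ratio | Planned power | New-findings power |
|---|---|---|---|---|
| 0.5% | 2.49% vs 3.48% | 1.40 | 74% | 82% |
| 2% | 3.96% vs 4.94% | 1.25 | 57% | 81% |
| 5% | 6.90% vs 7.85% | 1.14 | 37% | 80% |
| 10% | 11.8% vs 12.7% | 1.08 | 23% | 78% |

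From unrounded powers, the losses are about 7, 24, 43 and 54 points.

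**Sensitivity**
- Any abnormal ECG, assumed 40% at baseline, new 5% vs 7%: 0.40 + 0.60 × 0.05 = 0.430 and 0.40 + 0.60 × 0.07 = 0.442. Power is 19% against 83%.
- Larger effect, new 2% vs 4%: planned power is 98% at p0 = 2% and 68% at p0 = 10%; the new-findings test exceeds 99% in both.
- All 4800 per arm with an ECG, new 2% vs 3%, p0 = 10%: 27% against 85%.
- Only 80% of baseline findings persisting (simulation, 4000 per arm, p0 = 10%): 26% against 78%.
- Validity: with no treatment effect, the simulated rejection rate of the planned test was 4.8% to 5.2% for p0 from 2% to 30%.

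**The case against.** The strongest reply is that the rhythm and conduction objective is analyzed elsewhere. Protocol 10.2.2.7 says: "All events of supraventricular arrhythmias and cardiovascular conduction disorders will be prospectively collected and evaluated". Events the investigator considers clinically significant are recorded as SAEs, and SAP 4.17.1.2 analyzes this measure from SAE reports with incidence rates and a between-arm test, which fits an objective worded in terms of clinical significance. Other reported events enter the baseline-referenced TEAE analysis. Sites read every tracing and are asked to report significant ECG findings. For ischemia, protocol 10.2.3.3 adds: "All ECG findings of new, postbaseline MI/myocardial ischemia not clearly associated with a previously reported MI will be considered as a potential silent MI endpoint". All of this stands and narrows the gap. What remains is the finding that the reading center sees and the site does not report: section 10.2.3.3 describes notifying the site about new MI or ischemia but states no such route for rhythm or conduction findings.

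Second, each subcategory is compared separately. An old infarct or LV hypertrophy pattern dilutes its own row and the any-abnormal row, not a row for atrial fibrillation or conduction delay. That is right. The inclusion criteria therefore do not show that any rhythm or conduction finding is common at entry.

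Third, a reader might infer that the planned test misses most drug-induced rhythm or conduction changes. The documents do not support that. They give neither baseline prevalence nor new-finding rates, and the test keeps most of its power when the finding is rare at entry or the effect is larger. Nor is the comparison biased toward a false signal.

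Fourth, the ECG Charter is not among the documents, and its reading categories might include a new-finding code. That is possible, but neither analysis section uses one.

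**Conclusion.** The point holds as a loss of sensitivity in a supportive safety table. As written, both documents compare visit prevalence without reference to Visit 3, although the baseline ECG exists. On the assumed rates the loss runs from about 7 points of power at 0.5% baseline prevalence to about 54 points at 10%, and is about 64 points (19% against 83%) for any abnormal ECG in the 40% scenario. The true loss cannot be fixed from the documents.

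The practical consequence is confined mainly to centrally read rhythm and conduction findings that never become an AE or SAE. It would be wrong to read this as saying that the trial has no analysis of new rhythm events, or that the planned test is invalid.

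The calculation covers a single visit. The recommended analysis counts a new finding across several scheduled ECGs, which also picks up transient findings and reader variability. Its exact gain was not computed.

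**What to change.** In SAP 4.17.5, before unblinding, add a between-arm comparison for each category and subcategory: the number of patients with a new reading-center finding on a scheduled post-randomization ECG, among patients whose Visit 3 ECG lacks that finding, with relative risk and 95% CI. Report new findings that also draw on unscheduled ECGs as a supplementary count, because unscheduled tracings depend on clinical ascertainment. Keep the planned by-visit table; dropping its p-values would be a matter of preference and is not needed.

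The new definition depends on which ECGs are scheduled. SAP 4.17.5 describes an ECG at each visit, whereas protocol 7.1.4 and Attachment 1 list Visit 3, every 12 months and the final visit. These passages should be reconciled.

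The cost is SAP wording and one table, with no new data collection. The downside is that patients without a readable Visit 3 ECG, or with the finding at Visit 3, leave that finding's comparison.
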